Patients with underlying psychological illness have been reported to be at significantly greater risk of infection with and death from COVID-19 [1–3]. Previous work suggests specific drug classes, such as antipsychotics and antidepressants, are associated with an increased risk of respiratory infection, and death associated with that infection [4–6], though these findings may be associated with significant residual confounding [5]. Whether the associations of psychological illness with infection and death from SARS-COVID-19 are related to particular medication classes has not so far been determined.

Psychological illness prior to ICU admission has been poorly studied. However, use of Selective Serotonin Reuptake Inhibitors (SSRIs) prior to ICU admission has been associated with increased mortality, an effect related to the degree of re-uptake inhibition [7]. Whether prior psychological illness and use of particular classes of medication for these diseases is associated with ICU admission or outcome, either with COVID-19 or other severe acute respiratory infection has not been studied.

Previous SARS outbreaks have been associated with significant neuropsychological sequelae [8] In the United States, recent work has suggested that COVID-19 disease is associated with significant subsequent neuropsychological disease [3].

Prior to the COVID-19 outbreak, patients who have been admitted to an ICU had high incidences of subsequent neuropsychological sequelae [9] and ongoing cognitive impairment [10]. However, understanding the neuropsychological consequences of critical illness has been impaired by limited understanding of prior neuropsychological disease [11]. We will investigate whether neuropsychological sequelae of patients treated on an ICU with COVID-19 disease differ from those treated on ICU for different conditions, taking into account prior neuropsychological disease.

Hypothesis

We hypothesise that prior neuropsychological disease increases the risk of severe COVID-19 outcomes as with other acute respiratory disease and that this increase is associated with treatment with particular medication classes.

We hypothesise that infection with COVID-19 results in severe neuropsychological outcomes following treatment in hospital or on an ICU and that these outcomes differ in type and severity from neuropsychological outcomes seen following admission for SARI.

Aims

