This study will investigate neuropsychological disease and treatments before and after severe COVID-19 disease. The two main aims are:

1. to evaluate the associations of pre-existing neuropsychological diseases and treatments with severe COVID-19 outcomes in comparison to patients without pre-existing neuropsychological pathology;

2. to evaluate the associations between hospital or ICU admission due to COVID-19 and neuropsychological sequelae following discharge home in comparison to patients with ICU admission due to non-COVID-19 severe acute respiratory infections (SARI).

Objectives

- 1. To assess whether pre-existing neuropsychological diseases (by separate diseases and overall) are associated with severe COVID-19 outcomes (hospital and ICU admission and death) in comparison to the general population.
- 2. To assess whether pre-existing neuropsychological treatments (as a class and individually where possible) are associated with severe COVID-19 outcomes (hospital and ICU admission and death) and whether these explain disease associations in comparison to those not receiving such treatments.
- 3. To assess whether the risk of severe COVID-19 outcomes with prior neuropsychological disease differs from the risk of severe outcomes with SARI.

After discharge following a hospital admission for COVID -19 infection:

- 4. To assess the incidence of new neuropsychological diseases up to one year after hospital and ICU discharge following treatment for COVID-19 disease.
- 5. To compare the incidence of new neuropsychological diseases up to one year after hospital and ICU discharge with COVID-19 disease to the incidence following discharge after treatment for SARI.

Summary of the potential impact

This study will provide a better understanding of how pre-existing psychopathology and concomitant medication affect the risk of hospital and ICU admission and death due to COVID-19 and how any differences between those with and without preexisting psychopathology and COVID-19 infection compare to other severe acute respiratory infections. We will discover the neuropsychological sequelae of admission to a hospital or ICU with COVID -19 disease, taking into account prior neuropsychological disease and whether these differ from patients discharged from an ICU following SARI. These findings will be key to prevention and management of ongoing problems for these patients.

METHODS

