For cohort two, our primary outcome is the first occurrence of either hospital admission with SARI in the HES dataset (defined as a new ICD-10 code J09-J22 in the HES dataset) or ICU admission in the ICNARC CMP dataset with SARI (defined as any admission with unique diagnostic code any one of RE129 RE131 RE82 RE50 RE86 RE94 RE75 RE133 RE132 RE121 RE1 RE128 RE16 RE130 RE117 RE42 RE41) or death. Secondary outcomes will be each of these three events considered separately (I.e. SARI related hospital admission, ICU admission, death).

Aim 2.

Our primary outcome is development of new neuropsychological disease up to 1 year following hospital discharge which we define as having received a diagnostic code as below:

- Anxiety and stress-related disorders [ICD F40-48 and corresponding Read codes]
- Mood disorders [ICD F30-39 and corresponding Read codes]
- Psychotic disorders [ICD F20-29 and corresponding Read codes]
- Dementia [ICD F00-F03, G30, G31.0 ? and corresponding Read codes]

Secondary outcomes are the diagnosis of new neuropsychological disorders (as defined above) with treatment, and where numbers are available the new diagnosis with or without treatment of each class of disorders, each considered as a separate endpoint.

Neuropsychological treatments are defined as:

- Hypnotics and anxiolytics: (hypnotics, anxiolytics, barbiturates and methyprylone, benzodiazepines)
- Antidepressant drugs (Tricyclic and related antidepressant drugs, Monoamine-oxidase inhibitors, Selective serotonin re-uptake inhibitors, Other antidepressant drugs)
- Drugs used in psychoses and related disorders (Antipsychotic drugs and depot injections, Lithium salts, Phenothiazine derivatives)

Definition of exposures

Aim 1

Neuropsychological disease will be defined as an ordinal variable with the following three categories: no relevant diagnosis or drugs; diagnosis ever recorded without recent drug treatment; diagnosis present with recent drug treatment (with at least two prescriptions for neuropsychological treatments as above within the six months preceding study entry).

Our primary exposure is active neuropsychological disease on the study entry date which we define as having received a diagnostic code as above (24th January 2020 for cohort 1 and 24th January 2015 for cohort 2).

Aim 2.

The primary exposure is a hospital or ICU admission resulting from COVID-19 infection. Comparator exposures are hospital or ICU admission resulting from SARI.

Covariates

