For aim 1, the various different neuropsychological conditions of patients in cohort 1 are likely to result in varying levels of exposure to covid-19, compared to the populations without these conditions, with some conditions likely to have a protective effect, but in other conditions the reverse is expected. We have added a secondary analysis to examine the effect of specific conditions in order to evaluate this.

For aim 2, the two cohorts have experienced their exposure of interest (ICU admission with either COVID or SARI) during different time frames. Patients with SARI (admitted to ICU between 2015 to 2020) will have longer follow-up, but patients with COVID (admitted to ICU during 2020/21) may have benefited from the recently increasing public awareness of mental health conditions. To combat this, we have capped all follow-up at a maximum of 1 year post ICU discharge, and we will include a time-dependent covariate to assess whether risk varies with time post discharge. We have also included a cohort of patients with SARI admitted during 2020/21 for comparison with the COVID cohort during the same time frame.

We will derive the E-value to estimate the extent unmeasured confounding.

Study Size

For aim 1 we will use the entire QResearch database of approx. 8.3 million adult patients to maximise precision and minimise selection bias. We chose to use the last 5 years of ICNARC data for SARI comparisons to use recent data whilst having sufficient numbers for comparison taking into account the numbers from previous studies and after linkage [13, 14].

For aim 2, we will use all known ICU admissions from the ICNARC database for SARI and/or COVID who can be linked to the QResearch database. In cohort 3 the expected sample size is in the region of 11,000 admissions in total, for cohort 4 it is likely to be in the region of 7,000 admissions per year, and for cohort 5 around 3,500 patients.

Quantitative variables

Quantitative variables will be treated as continuous variables without categorisation. Descriptive summary statistics (mean and standard deviation, median interquartile range or number (%) as appropriate) will be used to present sociodemographic and clinical characteristics of patients with and without COVID-19 infection for those with and without neuropsychiatric conditions or treatments.

Statistical Methods

Aim 1.

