Cause-specific Royston Parmar flexible parametric models will be used to estimate the hazard ratios of developing new neuropsychological diseases after having received intensive care, comparing patients who received intensive care for COVID-19 (cohort 3) vs those who received intensive care for SARI (cohort 4). This model will adjust for all previously listed covariates. The age variable will be included as a restricted cubic spline rather than a linear term. Follow-up will start on the date of discharge from hospital.

Proportional hazards assumption will be tested, and time dependent terms will be included if the hazard ratio changes over time. A random frailty term will be included to account for similarities amongst patients admitted in the same critical care unit

A limited number of two-way interactions which are considered to be clinically or biologically plausible will be identified prior to analysis, and tested using a Wald test.

Primary care data on some potential confounding variables is incomplete (e.g. smoking status, alcohol intake, ethnic group, BMI). Reason for admission is mandatory for all records in the ICNARC database (the core dataset for aim 2), so classification of these reasons as either SARI or COVID related will be non-missing for all patients. Only admission records for completed critical care stay (non-missing length of stay and survival status at end of critical care) will be included (n.b. outcomes are missing in <1% of COVID ICU admissions to date). Remaining variables from the critical care stay are use of sedation in the first 24 hours, and duration of advanced respiratory support, which are missing for a small number of patients (<1.5%).

Both aims.

To allow data analysis with all eligible patients, we will impute missing data in all cohorts. We will use multiple imputation with chained equations under the missing at random assumption to replace missing values and use these values in our main analyses [15]. We will include all exposure and confounding variables in the imputation model, along with the Nelson–Aalen estimator of the baseline cumulative hazard, and the outcome indicator. We will carry out five imputations. Analysis models will be fitted in each imputed dataset and Rubin's rules to will be used to combine the results across the imputed datasets.

As the analyses are on time to event data, patients will be censored at the date when they are lost to follow-up as defined in cohort definitions above.

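### Aim 2 hypothesises that sequelae after COVID-19 differ in type from those after SARI, but the protocol contains no estimate or test of whether the hazard ratio differs between disorder classes

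*Protocol*

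**What the plan says.** The Hypothesis section of the protocol expects that "these outcomes differ in type and severity from neuropsychological outcomes seen following admission for SARI".

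Objective 5 is narrower: "To compare the incidence of new neuropsychological diseases up to one year after hospital and ICU discharge with COVID-19 disease" with the incidence after SARI. It does not mention type.

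Under Definition of outcomes, Aim 2, "Our primary outcome is development of new neuropsychological disease up to 1 year following hospital discharge". This pools anxiety and stress-related disorders, mood disorders, psychotic disorders and dementia. The classes return only among the secondary outcomes: "where numbers are available the new diagnosis with or without treatment of each class of disorders, each considered as a separate endpoint".

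The Aim 2 part of Statistical Methods states: "Cause-specific Royston Parmar flexible parametric models will be used to estimate the hazard ratios of developing new neuropsychological diseases after having received intensive care". The contrast is cohort 3 (COVID-19) against cohort 4 (SARI, 2015-2020). On interactions: "A limited number of two-way interactions which are considered to be clinically or biologically plausible will be identified prior to analysis", to be tested with a Wald test.

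Sensitivity analyses adds a competing-risk analysis for death and a propensity-weighted analysis of any new condition.

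**The concern.** The natural reading of a difference in type is that the mix of the four classes is not the same after COVID-19 as after SARI. In the plan's own measure, this means that the COVID-versus-SARI hazard ratio is not equal across classes. A pooled hazard ratio cannot show that. Four separate hazard ratios show it only if they are compared with one another, and no such comparison is planned.

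Without it, the easiest summary is a list of which classes differ significantly. That list depends heavily on how common each class is. Anxiety and mood disorders would tend to reach significance, and dementia and psychosis would tend not to, even if COVID-19 raised all four by the same factor. At stake is whether any statement about type rests on a direct comparison or on differing precision.

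**Working it through.** **Is there a matching analysis?** Taking the planned Aim 2 analyses in turn:

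- Pooled primary model: one hazard ratio over all classes, so no information on type.
- Class endpoints: each analysed separately, with no contrast between them.
- Two-way interactions: not named. In a model for a single endpoint they act between covariates; outcome class becomes a covariate only if the data are stacked, which is not planned.
- Competing-risk analysis: concerns death.
- Propensity-weighted analysis: concerns any new condition.

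None compares class hazard ratios.

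**How much could this matter?** The protocol states no power, alpha, expected hazard ratio or event rate for Aim 2, so there is no figure to reproduce.

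Inputs from the Study Size section: "In cohort 3 the expected sample size is in the region of 11,000 admissions in total"; cohort 4 has about 7,000 a year, and 7,000 x 5 = 35,000.

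Assumptions:
- One-year SARI risks p for anxiety / mood / dementia / psychosis: 4 / 3 / 1 / 0.3% (set A) or 2 / 2 / 0.7 / 0.2% (set B).
- The same true hazard ratio (HR) in every class.
- Independent classes and a two-sided 5% level.

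Formulas, per class:
- SE(log HR) = sqrt(1/(11,000 x p x HR) + 1/(35,000 x p)).
- Power = Φ(log HR/SE − 1.96) + Φ(−log HR/SE − 1.96).
- P(mixed pattern) = 1 − P(all significant) − P(none significant).

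Example, HR 1.3, set A:
- Anxiety: 572 and 1,400 events, SE 0.050, power 1.00.
- Psychosis: 42.9 and 105 events, SE 0.181, power 0.31.
- All four powers (anxiety, mood, dementia, psychosis): 1.00, 0.996, 0.75, 0.31. Their product is about 0.23 and P(none) is about 0, so P(mixed) = 0.77.

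Set B at HR 1.3: powers 0.96, 0.96, 0.60, 0.22. P(all) = 0.12 and P(none) is below 0.001, so P(mixed) = 0.88.

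| Common HR | Mixed, four classes | Mixed, without psychosis |
|---|---|---|
| 1.0 | about 19% | about 14% |
| 1.2 | 93-94% | 64-78% |
| 1.3 | 77-88% | 25-44% |
| 1.5 | 35-54% | 1-5% |
| 2.0 | 1-5% | under 1% |

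**Sensitivity to the assumptions.**
- Other risk sets (anxiety / mood / psychosis / dementia from 1 / 1.5 / 0.1 / 0.3% up to 6 / 8 / 0.6 / 1.5%): 82-95% at HR 1.2, 52-96% at 1.3 and 0-28% at 2.0.
- All four classes at 3%: 42% at HR 1.2 and 2% at 1.3.
- Only the two common classes, same other risk sets: at most 51%.
- Correlation of 0.2 to 0.4 between class estimates, sets A and B: 82-91% at HR 1.2 and 73-85% at 1.3.
- Cohort 5 (about 3,500) as comparator, sets A and B: 57-75% at HR 1.2, 82-94% at 1.3 and 88-94% at 1.5.
- Significant effects in opposite directions: under 1% throughout.

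**With a direct test.** A 3-degree-of-freedom test of equal class hazard ratios signals a difference in about 5% of studies when the effect is common. From a noncentral chi-square with sets A and B, its power is 83-97% if anxiety has HR 1.5 and the others 1.1, and 54-72% if dementia has HR 1.5 and the others 1.1.

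**The case against.** The strongest case on the other side has four parts.

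1. The statistical analysis plan is not shown and may contain a between-class test, which is detail that a protocol can leave to it. This stands in part: one cannot say that the study will lack the test. But the protocol writes out its own methods for Aim 2 and fixes how the classes are handled, namely separately, while stating a hypothesis that this handling does not address. That mismatch lies within the document.

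2. A reader might infer that the plan leaves the hypothesis to a comparison of p-values and will therefore usually report a false difference in type. The documents do not support this. No alpha is stated, no rule says that type will be judged by significance, and class hazard ratios with intervals could be compared by eye. The probabilities above are conditional on a rule that the protocol does not contain.

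3. The figures rest on assumed risks, and class endpoints are analysed only where numbers allow. Psychosis, with 22 to 33 COVID-19 events at HR 1 (11,000 x 0.2% to 0.3%), is the class most likely to be dropped. This stands, and it lowers the figures considerably. The cohort sizes are also admissions, not reduced for survival to discharge or prior disease.

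4. Equality of hazard ratios is one way to formalise type and is not the protocol's wording. True, but the protocol offers no other, and its only typology is the four classes.

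**Conclusion.** The point holds in limited form. The hypothesis on type has no matching estimate, interval or test in the protocol, and this does not depend on any assumed rate.

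The risk of a misleading reading is conditional. If the class results were judged by significance, a common effect would often give a mixed pattern at hazard ratios of about 1.2 to 1.3 when classes of very unequal frequency are all analysed. It would not do so with no effect, with a large effect against cohort 4, or from about 1.3 upward once psychosis is left out. A claim that a common effect will usually look like a difference in type goes further than the documents allow.

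The gap is worth closing. It does not touch the pooled primary analysis or the comparison of incidence in Objective 5.

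**What to change.** Choose one of two changes.

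**Add a between-class comparison.** Fit one stacked marginal multiple-endpoint model with one row per patient per class. The classes are not mutually exclusive, so a competing-causes layout would not fit. Include:
- class-specific baselines and covariate effects;
- COVID-by-class terms;
- a variance that allows for repeated rows per patient and for critical care unit;
- a rule, fixed before analysis, for grouping or leaving out rare classes.

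Report the joint Wald test of equal class hazard ratios and the ratios of class hazard ratios with 95% intervals, and base any statement about type on these.

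**Or narrow the hypothesis.** Restrict the Hypothesis section to incidence, in line with Objective 5, and present the class results as descriptive.

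The first option costs a paragraph and one extra secondary model on data already being prepared. Specifying the clustering at both levels takes some care, and power for rare classes is limited. The second costs a sentence. Neither needs new data.

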A retrospective cohort data linkage study of patients aged 18 years and above registered in English general practices. This protocol is written following RECORD guidance [12].

Settings Describe the setting, locations, and relevant dates, including periods of recruitment, exposure, follow-up, and data collection.

1205 general practices in England contributing to the QResearch database, which is nationally representative. We defined cohorts during the COVID pandemic as between 24th January 2020 (the date of the first confirmed COVID-19 case in England) and study end (30th June 2021). We defined retrospective comparison cohorts as the 5 years prior to this date (24th January 2015- 23rd January 2020).

Data linkage

The study will include adult patients registered with the QResearch database. Practices must have been contributing to the QResearch database for at least 12 months. For the investigation of associations of pre-existing neuropsychological diseases and treatments (cohort 1) patients must be registered for at least a 12-month period before 24th January 2020. For the investigation of incidence of new neuropsychological diseases (cohort 2) patients must be registered for at least a 12-month period between January 2015 to 2020. The date of study entry is separately defined below for each study cohort.

Patients in QResearch will be linked to: (1) the ICNARC Case Mix Programme (CMP) database, the national clinical database from adult critical care; (2) the Hospital Episode Statistics (HES) data warehouse containing records of all patients admitted to NHS hospitals and Emergency departments in England; (3) the national registry of COVID-19 RT-PCR positive test results from Public Health England (PHE); and (4) Office of National Statistics COVID-19 mortality data, which includes all deaths due to COVID-19 in England. Data linkage will be based primarily on NHS number. For a description of the datasets see Supplemental material S1.

Participants

Give the eligibility criteria, and the sources and methods of selection of participants. Describe methods of follow-up. The methods of study population selection (such as codes or algorithms used to identify subjects) should be listed in detail.

Aim 1.

From the linked dataset, we will extract two cohorts to explore the association between neuropsychological diseases and treatments and hospitalisation, ICU admission or death:

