- oral steroids

Intensive care stay (Aim 2)

- Length of stay
- Duration of advanced respiratory support (invasive ventilation)
- Use of sedation in the first 24 hours of admission

Effect Modifiers

For aim 1, we assessed these potential confounders by creating directed acyclic graphs (DAG) to determine which variables were likely to be to some extent caused by the presence of prior neuropsychological disorders (as the exposure of interest), and which were not likely to be caused by the presence of prior neuropsychological disorders, but were thought to be independently potential predictors of severe Covid outcomes.

Variables from the above list to be included in the model are all those grouped under: demographics; co-morbidities; lifestyle factors; plus prescription of any immunosuppressants and/or anticoagulants. Other medications (as these are not believed to affect the risk of severe Covid outcomes), and in-hospital factors (length of stay and use of sedation during intensive care admission, as these are outcomes potentially caused by Covid severity) will not be adjusted for.

For aim 2, our exposure of interest is admission to intensive care with SARI (compared to admission to intensive care with SARI. This exposure occurs at a fixed time which is used as the baseline for our time to event analysis in predicting the outcome of interest, and all other variables listed above are measured before this baseline. Therefore (depending on the available sample size and number of events), all the previously listed covariates of interest may be included in our adjusted models.

Data sources

Intensive Care Unit admission data will come from the ICNARC CMP dataset Hospital admission and mortality will come from the HES dataset

All exposures and confounders and neuropsychological outcomes will come from the QResearch database.

COVID-19 infection test status will come from the national registry of COVID-19 RT-PCR positive test results from Public Health England (PHE).

Bias

To limit the possible impact of COVID-19 testing bias (collider bias) we will analyse the entire QResearch eligible population, rather than restricting analysis to only those with a positive COVID-19 test.

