Royston Parmar flexible parametric survival models will be used to estimate the hazard ratio of severe COVID-19 outcome (hospital or critical care admission and death) in cohort 1 for patients with neuropsychological disease at study entry compared with those without disease, and for individual neuropsychological diseases and treatments.

This analysis will be adjusted for the listed covariates. The age variable will be included as a restricted cubic spline rather than a linear term. Before commencing analysis, we will assess the numbers of patients with each comorbidity, and may if necessary group the presence of certain less common comorbidities together. Any such grouping will be done on the basis of clinical similarities only and prior to examining any outcomes by comorbidity. We may also include a time-varying binary covariate to record any new diagnosis and/or treatment which occurs after study entry in patients originally free from both diagnosis and treatment, depending on the number of these events. Proportional hazards assumptions will be tested, and time dependent terms will be included if the hazard ratio changes over time (I.e. if the association between neuropsychological disease and risk of severe COVID-19 has changed during the course of the pandemic). A random frailty term will be included to account for similarities amongst patients registered in the same primary care practice. Possible interactions between exposure and age, sex and ethnicity will be considered and tested using a Wald test.

The same methods will be used for secondary analyses in which the main exposure variable will be defined as either the presence of a specific class of neuropsychological disorder or any other neuropsychological disorders or no disorder.

The primary analysis will be used to estimate the hazard ratio of severe SARI outcomes in cohort 2 using the same exposure variables.

If non-proportional hazards are observed in either cohorts 1 or 2, then maximum follow-up time will be capped at 1 year and a time-dependent covariate will be added to the analysis of both cohorts to maintain the comparability of results.

Aim 2.

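### The Aim 2 model accounts for critical care unit but not for GP practice, although practices record the outcome; bias arises only if practices' coding habits track their COVID:SARI mix

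*Protocol*

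**What the plan says.** - **Aim 2 cluster term** (Protocol, Statistical Methods, Aim 2): "A random frailty term will be included to account for similarities amongst patients admitted in the same critical care unit". No section adds a practice term for Aim 2.
- **Aim 1 cluster term** (Statistical Methods, Aim 1): "A random frailty term will be included to account for similarities amongst patients registered in the same primary care practice".
- **Aim 2 outcome** (in the Variables section): "Our primary outcome is development of new neuropsychological disease up to 1 year following hospital discharge which we define as having received a diagnostic code". The secondary outcomes build on the same diagnoses, with treatment added.
- **Source of that outcome** (Data sources): "All exposures and confounders and neuropsychological outcomes will come from the QResearch database". The Settings section describes this source as "1205 general practices in England contributing to the QResearch database, which is nationally representative".
- **Adjustment** (Statistical Methods, Aim 2): "This model will adjust for all previously listed covariates". The Covariates section lists region, deprivation, ethnicity, domicile, household size, lifestyle and comorbidity, but nothing about the practice or its recording habits. The propensity score in the Sensitivity analyses uses the same list.

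**The concern.** The practice term is present in Aim 1, where hospital, intensive care and mortality data supply the outcome. It is absent in Aim 2, where practices record the outcome. How readily a practice enters a code for anxiety, depression or dementia acts directly on the Aim 2 event rate. One critical care unit takes patients from many practices, so a unit frailty can absorb only what a whole catchment shares.

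Suppose practices with a high share of COVID-19 survivors also coded more, or less, readily than other practices feeding the same units. Part of that difference would then be read as an effect of COVID-19. The other planned safeguards do not deal with this. Cohort 5 addresses calendar time. The E-value describes how strong unmeasured confounding would have to be, but does not remove it.

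**Working it through.** The protocol gives no event rate, effect size or between-practice variance for Aim 2, so there is no figure of its own to reproduce.

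**1. Does exposure vary within practices?** From Study Size, cohort 3 is about 11,000 and cohort 4 about 7,000 a year for 5 years = 35,000. Settings gives 1,205 practices. Treating the expected admissions as linked patients:
- total per practice: (11,000 + 35,000)/1,205 ≈ 38
- COVID-19: 11,000/1,205 ≈ 9; SARI: 35,000/1,205 ≈ 29

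A typical practice contributes to both sides, so its coding habit acts on both arms.

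**2. When does coding bias the hazard ratio?** Let s be the SD across practices of the log coding rate, t the SD of the log-odds that a patient is a COVID-19 patient, and r their correlation. Relative to SARI patients, COVID-19 patients are drawn from practices whose mean log coding rate is higher by about r·s·t. The bias factor is therefore about exp(r·s·t). All three inputs are assumptions.
- r = 0: 1.00, whatever s and t
- s = t = 0.3, r = 0.3: exp(0.027) = 1.03
- s = 0.4, t = 0.5, r = 0.2: exp(0.04) = 1.04
- s = 0.4, t = 0.5, r = 0.3: exp(0.06) = 1.06
- s = t = 0.5, r = 0.5: exp(0.125) = 1.13

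**3. Which practice term removes it?** Poisson simulation, true HR 1, 11,000 versus 35,000 patients, 1,205 practices, no unit term (300 runs; 40 for the random-term column):

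| Event rate | s = t | r | No practice term | Practice random term | Conditional on practice |
|---|---|---|---|---|---|
| 5% | 0.5 | 0 | 1.002 | 0.998 | 1.001 |
| 5% | 0.3 | 0.3 | 1.028 | 1.020 | 1.001 |
| 5% | 0.5 | 0.3 | 1.068 | 1.049 | 0.996 |
| 5% | 0.5 | 0.5 | 1.123 | 1.076 | 0.996 |
| 15% | 0.5 | 0 | 0.999 | 0.998 | 0.999 |
| 15% | 0.5 | 0.5 | 1.126 | 1.044 | 1.001 |

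With r = 0 the ratio of the empirical SD to the model standard error was 0.90–1.08 without any practice term, so the standard error is not materially wrong either. With r above 0 a random term removes only part of the shift; conditioning on practice removes it.

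**4. With a unit term and a practice covariate.** Simulation with 46,000 patients, 1,205 practices, 200 units as fixed effects, s = 0.4, t = 0.5, 8% event rate, true HR 1.20, 200 runs per row. The covariate is a single background coding rate per practice:

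| r | Unit only: HR (95% interval coverage) | Plus practice rate: HR (coverage) |
|---|---|---|
| 0 | 1.203 (96%) | 1.203 (96%) |
| +0.2 | 1.242 (81%) | 1.202 (94%) |
| −0.2 | 1.162 (84%) | 1.198 (97%) |
| +0.3 | 1.260 (74%) | 1.202 (92%) |
| −0.3 | 1.144 (75%) | 1.199 (91%) |

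The unit-only shifts are 1.242/1.20 = 1.035 and 1.260/1.20 = 1.05 upward, and 1.162/1.20 = 0.97 and 1.144/1.20 = 0.95 downward. The standard error of the log HR was about 0.036 with or without the covariate, so the shift is about one standard error at r = ±0.2 and somewhat more at ±0.3. Such a rate is well estimated: 8.3 million adults/1,205 ≈ 6,900 per practice.

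**5. Why the rate must be fixed in time.** Cohort 4 was admitted up to 23 January 2020 and cohort 3 from 24 January 2020, so their admission periods do not overlap. If background coding fell by 10% or 20% in the pandemic but coding of intensive care survivors did not (assumed), a year-specific rate would move a true HR of 1.20 to about 1.20/0.9 = 1.33 or 1.20/0.8 = 1.50. Simulation gave about 1.31–1.33 and 1.49. That far exceeds the shift being corrected.

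**The case against.** The strongest reply is that critical care unit is a defensible cluster. Aim 2 compares intensive care admissions, and the protocol treats the ICNARC data as the core dataset for that aim. In Aim 1 most patients never enter a unit and the exposure is itself a GP-recorded diagnosis, so practice is the natural cluster there. The frailty is also meant to handle similarity between patients, not confounding. This stands as a reason for keeping the unit term. It does not explain leaving out the level at which the outcome is recorded.

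A second reply is that the planned adjustment is mostly at patient level and may absorb much of any link between coding and case mix. The simulations contain none of those covariates, and the r that matters is what remains after adjustment. That stands, and it is why the sizes above are illustrations and not estimates.

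A reader might infer that differences in coding between practices necessarily remain in the COVID-versus-SARI hazard ratio. The documents do not support that. Both cohorts are drawn from the same practices, the shift is nil at r = 0, and nothing in the protocol shows that r differs from 0. Nor can one infer that the planned standard errors are materially too small.

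**Conclusion.** The mismatch is real. Aim 2 takes its outcome from practice records but has a cluster term only for critical care unit, while Aim 1 has the practice term. Its consequence is conditional: no bias if coding propensity and COVID:SARI mix are unrelated across practices after adjustment, and a shift of roughly 3–6% in either direction at assumed correlations of 0.2–0.3 with spreads of about 0.3–0.5. In the unit-only simulation, coverage fell to about 74–84% at those correlations. None of r, s, t or the event rate can be read from the documents. Severity is minor: an inexpensive improvement, not a flaw that undermines the comparison.

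**What to change.** Keep the critical care unit frailty. Add one analysis that accounts for practice and report it beside the main Aim 2 result:
- preferably, stratify by (condition on) GP practice;
- or adjust for each practice's log rate of new neuropsychological codes among its registered adults, measured once over a fixed period before 24 January 2020. This rate also reflects true local morbidity, which should be acknowledged when the result is interpreted.

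Do not use a rate specific to the calendar year of discharge, for the reason in step 5 of the working. A practice random term (crossed with unit) or standard errors clustered on practice may be added for dependence, but neither is the remedy for this bias: the random term removes only part of it, and clustered standard errors leave the hazard ratio unchanged.

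The cost is a sentence in the analysis plan, a practice identifier or one derived covariate from QResearch data already held, and one more model fit. Stratification makes the standard error about 4% larger; the fixed-rate covariate left it unchanged in simulation.
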